 DEATH	 LIFE-THREATENING	 INVOLVED OR PROLONGED HOSPITALIZATION	 CONGENITAL ANOMALY	 PERSISTENT OR SIGNIFICANT DISABILITY OR INCAPACITY
 MEDICALLY SIGNIFICANT precise: _____				

3. Relevant Medical History				
_____				

4. Serious Adverse Event				
Reaction start date	[REDACTED]	Date of Hospitalization (if applicable)	[REDACTED]	[REDACTED]
Description Include a history of the event chronologically including: signs and characteristics, severity, dates and outcome of hospitalization and any other relevant information not captured elsewhere on the form				
Chronological data relevant for the SAE:	Date of inclusion	[REDACTED]	Date of first administration of study drug	[REDACTED]

**5. Non Serious event of special interest**

No  
 Yes – Specify below

*Use only in exceptional circumstances to indicate when a non-serious event of special interest (as defined by the protocol) is being reported:*

**6. Serious adverse Event Outcome**

**SERIOUS CRITERIA:**

Date

FATAL  
 RESOLVED  
 RESOLVED WITH SEQUELAE  
 IMPROVED  
 PERSISTING  
 WORSENED  
 UNKNOW

Sequelae : \_\_\_\_\_

**7. Study drug(s)**

*All study treatments specified in the protocol*

Name	Dose	Batch Number	Frequency	Route	Start date	End date	Ongoing

Delay of occurrence after last dose intake: 

--	--	--

 (time unit)

**8. Action taken with study drug(s)**

Name	No change	Temporarily interrupted		Ongoing	Dose adjusted (detail)	Unknow
		Date stopped	Date restarted			
						
						
						
						
						

In case of re-administration, did the reaction recur?  Yes  No

**9. Concomitant treatment**

Name	Daily dose	Route	Start date	End date	Ongoing	Indication
			□□□□□□	□□□□□□		
			□□□□□□	□□□□□□		
			□□□□□□	□□□□□□		
			□□□□□□	□□□□□□		
			□□□□□□	□□□□□□		

**10. Corrective treatment (drug, procedure, etc.)**

Name	Total daily dose	Start date	End date	Ongoing
		□□□□□□	□□□□□□	
		□□□□□□	□□□□□□	
		□□□□□□	□□□□□□	
		□□□□□□	□□□□□□	
		□□□□□□	□□□□□□	

**11. Relevant Laboratory / Diagnostic Tests**

Rq: Include laboratory values preceding the event

Details of additional tests can be completed on the Additional Laboratory / Diagnostic Tests form.

Additional form provided?  No  Yes (Number of extra-pages: \_\_\_\_)

Name of the test	Results (units)	Normal values / Reference ranges	Sample collection date	Result pending
			□□□□□□	
			□□□□□□	
			□□□□□□	
			□□□□□□	
			□□□□□□	
			□□□□□□	

**12. Possible causes of the event**

Check off all that apply	Specify
Pre-existing / underlying disease	
Study treatment	
Other treatment	
Protocol-related procedure	
Other (e.g. accident, new or intercurrent illness)	

**13. Investigator**

SAE Form	Full name (in uppercase letters)	Function	Date	Signature
Filled out by:			□□□□□	
Validated by:			□□□□□	

**14. AAA PV department**

SAE Form	Full name (in uppercase letters)	Function	Date	Signature
Reception by:			□□□□□	
QC by:			□□□□□	

**15. AAA Comments**

WHO DDE	World Health Organization Drug Dictionary

2 INTRODUCTION

The purpose of this statistical analysis plan (SAP) is to provide a detailed description of the planned analyses of safety and tolerability data that have been outlined in the clinical study protocol AAA 1002.

This SAP is based on the AAA 1002 Protocol Amendment n°4 dated 16 December 2014, entitled “Phase I-IIa study of safety, tolerance, pharmacokinetics, dosimetry and benefice of early nuclear medicine imaging of $99mTc$ -rhAnnexin V-128 in patients with rheumatoid arthritis or ankylosing spondylitis”.

This plan provides the basis for the statistical sections of the AAA 1002 clinical study report as described in the E3 Guideline on the Structure and Content of Clinical Study Reports issued by the International Conference on Harmonisation of Technical Requirements for Registration of Pharmaceuticals for Human Use (ICH).

This SAP was finalized before final lock of the database as per the E9 ICH Guideline on Statistical Principles for Clinical Trials.

3 STUDY OBJECTIVES

This Phase I-IIa study will be undertaken to determine the safety, tolerability, bio-distribution and ability of early imaging with $99mTc$ -rhAnnexin V-128 to predict response to treatment in 20 patients with diagnosed rheumatoid arthritis (RA) or ankylosing spondylitis (AS).

The objectives of this study are:

- To determine the safety and tolerability of imaging with $99mTc$ -rhAnnexin V-128.
- To determine the biodistribution, pharmacokinetics and radiation dosimetry of $99mTc$ -rhAnnexin V-128
- To demonstrate the time-dependent distribution and localization of $99mTc$ -rhAnnexin V-128 both in RA and AS patients
- To determine ability of early imaging with $99mTc$ -rhAnnexin V-128 to evaluate the presence of lesions before and after short term treatment of either RA or AS patients

4 STUDY DESIGN

4.1 Overall Study Design

This is a monocentric, open label, Phase I-IIa study. Patients who have signed the informed consent and are eligible for study participation according to the inclusion and exclusion criteria will receive a single intravenous bolus of $99mTc$ -rhAnnexin V-128 on Day 1 and a single intravenous bolus of $99mTc$ -rhAnnexin V-128 6 weeks later (+/- 2 weeks). All patients will start a new RA or AS treatment on Day 2 (Figure 1). In order to minimize the risks for the study population, patients will be enrolled with a minimum of 2-week interval.

Study duration is of 4 months +/- 2 weeks (including the screening period). Eligible patients will receive two injections: one on Day 1 and a second administration 6 weeks +/- 2 weeks later. The end of the study is defined as the moment that the last enrolled patient has completed 18 days follow-up after completing the second $99mTc$ -rhAnnexin V-128 administration. An

additional blood sample for immunological assay is required 3 months after the first administration of the ^{99m}Tc -rhAnnexin V-128 (Day 90 ± 14 days) in case of positive anti-Annexin antibodies outcome in previous examination.

[figure not shown]

Figure 1: Study flowchart (*: up to 10 patients)

4.2 Expected Sample Size

The number of patients in this study is not based on statistical power considerations. The planned sample includes 20 patients with Day 56 assessments which are believed to provide sufficient data to assess the general safety and tolerability of ^{99m}Tc -rhAnnexin V-128. Patients will be recruited with a ratio of 1:1 RA:AS. Any patient who has not completed Day 56 assessment will be replaced by a patient from the same group (RA or AS). It is expected that about 10% of patients will not complete their Day 56 assessments; therefore, approximately 23 patients will be recruited. In addition, 10 patients enrolled in the study will be asked to participate in a dosimetry and PK study, irrespective of the group they are part of (RA or AS). Out of the first 6 patients, at least 3 patients must take part in the dosimetry and PK sub-study.

Considering the very slow recruitment rate of this study, AAA, the sponsor decided to stop study recruitment by end of September 2017. With an 80% or more of the planned sample size evaluable for analysis, the sample size is still considered to be sufficient for assessing the primary objective. Regarding secondary objectives, a thorough data review will be organised before finalizing the SAP in order to assess the relevance of conducting all or part of the corresponding statistical analyses.

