### **Sample size**

The number of patients in this study is not based on statistical power considerations. The planned sample includes 20 patients with Day 56 assessments which are believed to provide sufficient data to assess the general safety and tolerability of 99mTc-rhAnnexin V-128. Patients will be recruited with a ratio of 1:1 RA:AS.

Any patient who has not completed Day 56 assessment will be replaced by a patient from the same group (RA or AS). It is expected that about 10% of patients will not complete their Day 56 assessments; therefore, approximately 23 patients will be recruited.

In addition, 10 patients enrolled in the study will be asked to participate in a dosimetry and PK study, irrespective of the group they are part of (RA or AS).

Out of the first 6 patients, at least 3 patients must take part in the dosimetric and PK sub-study.

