## **Vital Signs and ECG**

Vital signs will be taken at each study visits, while twelve-lead ECG will be performed.

Descriptive statistics (N, mean, median, minimum, maximum, 95% confidence interval for the mean, etc.) of the observed values as well as for the changes from baseline value will be created. Frequency tabulations with values within, below or above the normal ranges will be made.

ECG parameters will include heart rate (HR), RR interval, PR interval, QRS width and QT interval.

QT intervals will be corrected for heart rate. ECG results will also be evaluated by means of descriptive statistics (mean, median, 95% confidence interval for the mean, etc.) and frequency tabulations.

Graphical presentations might be created to facilitate the interpretation.

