7.11 Vital Signs

Summary statistics (n, mean, SD, median, quartiles, minimum, maximum) of vital signs will be presented at each assessment time point. Summary statistics of changes from baseline will also be presented.

Number and percentage of subjects with shift changes from baseline will be tabulated in Shift Tables for each vital sign assessment.

The following normal ranges for vital signs will be used:

Systolic blood pressure	BETWEEN 90 AND 150 (mm Hg)
Diastolic blood pressure	BETWEEN 45 AND 90 (mm Hg)
Heart Rate	BETWEEN 40 AND 100 (beats/min)

Listings of all vital signs will be presented.

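### The SAP omits, without declaring it, the protocol's 95% confidence intervals for mean vital signs and ECG; separately, it calls the reduced sample adequate for safety with no precision figure and no interval for adverse-event proportions

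*SAP*

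**What the plan says.** **Intervals for means.** For vital signs, protocol section 8 (Vital Signs and ECG) lists N, mean, median, minimum and maximum, and then "95% confidence interval for the mean, etc.) of the observed values as well as for the changes from baseline value will be created". The same section names the 95% interval for the mean again for ECG results. SAP 6.1 places changes from baseline in ECG parameters and in vital signs among the primary safety endpoints.

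SAP 7.11 reads: "Summary statistics (n, mean, SD, median, quartiles, minimum, maximum) of vital signs will be presented at each assessment time point". SAP 7.10 uses the same list for ECG parameters. Both sections also promise summary statistics of change from baseline. No interval appears there, in the default statistics for continuous variables (SAP 7.1.1), or in the shells for Tables 14.3.8.1 and 14.3.9.2. SAP 7.19 declares that the planned analysis was not changed.

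**Sample size and adverse events.** SAP 4.2 says "The number of patients in this study is not based on statistical power considerations", and then "The planned sample includes 20 patients with Day 56 assessments which are believed to provide sufficient data to assess the general safety and tolerability". It goes on to report that the sponsor ended recruitment by the end of September 2017 because accrual was very slow. "With an 80% or more of the planned sample size evaluable for analysis", it concludes, "the sample size is still considered to be sufficient for assessing the primary objective". It gives neither a final number nor a precision figure. Under SAP 7.8.1, adverse-event occurrence is the number of subjects affected divided by the Safety Set. Tables 14.3.1.1 and 14.3.1.2 show counts and percentages for RA, AS and total, without intervals. The protocol's adverse-event section also promises tabulation only.

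**The concern.** The first issue is traceability. The protocol named a statistic for primary endpoints, the SAP does not produce it, and the section meant to record such departures records none. A study report built on the SAP would repeat that statement.

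The second issue is what the primary result can tell a reader. In a small, untested, descriptive safety study, the main quantitative content of a zero or low count is the range of true rates it leaves open. SAP 4.2 gives a judgement of adequacy in place of that range, and the adverse-event tables do not supply it. Because the tables are split by disease, the displayed denominators will be smaller still. The SAP's initial version is dated 26/01/2018, after the recruitment stop, so the achieved number and its precision could have been stated.

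**Working it through.** **Inputs**
- Planned evaluable number: 20 with Day 56 assessments (SAP 4.2).
- Ratio: "Patients will be recruited with a ratio of 1:1 RA:AS" (SAP 4.2), so 10 + 10 as planned.
- Recruitment target: "It is expected that about 10% of patients will not complete their Day 56 assessments; therefore, approximately 23 patients will be recruited" (protocol, Sample size).
- Reduced sample: at least 0.80 × 20 = 16 evaluable (SAP 4.2). The actual number is not given, so 16 is an assumed floor.
- Adverse-event denominator: the Safety Set, meaning eligible subjects dosed at least once (SAP 7.3, 7.8.1). It can exceed the number with Day 56 data.

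**The plan's own figure.** 20 / (1 − 0.10) = 22.2, rounded up to 23. This reproduces. The 20 is a judgement with no formula behind it, so there is nothing to recompute.

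**Intervals for means.** The check here is a comparison of texts:
- Vital signs: the protocol names a 95% interval for observed values and for changes; SAP 7.11 and Table 14.3.8.1 have none.
- ECG: the protocol names a 95% interval for the mean; SAP 7.10 and Table 14.3.9.2 have none.
- SAP 7.19: no change declared.

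The half-width of the omitted interval, in SD units, is t(0.975, n − 1) / √n:
- n = 16: 2.131 / 4 = 0.53 SD
- n = 20: 2.093 / 4.472 = 0.47 SD

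**Upper limit for zero events.** One-sided 95%: 1 − 0.05^(1/n). Two-sided 95% (Clopper-Pearson): 1 − 0.025^(1/n).

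| Observed | Two-sided upper limit | One-sided upper limit |
|---|---|---|
| 0/16 | 20.6% | 17.1% |
| 0/20 | 16.8% | 13.9% |
| 0/8 (one disease group, if 16 split 1:1) | 36.9% | 31.2% |
| 0/10 (one disease group as planned) | 30.8% | 25.9% |

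**One event.** The two-sided exact 95% interval is 0.2% to 30.2% for 1/16 and 0.1% to 24.9% for 1/20.

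**Chance of seeing at least one case**, 1 − (1 − p)^n:
- true rate 10%: 1 − 0.9^16 = 81.5%; 1 − 0.9^20 = 87.8%
- true rate 5%: 1 − 0.95^16 = 56.0%; 1 − 0.95^20 = 64.2%

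**Share due to early stopping.** Going from 20 to 16 adds 20.6 − 16.8 = 3.8 percentage points to the two-sided limit (17.1 − 13.9 = 3.2 one-sided). The limit was already 16.8% at the planned size.

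**The case against.** The strongest defence is that no information is lost. The shells print n, mean and SD, from which the interval for a mean follows directly, and the adverse-event tables print N and n (%), from which the exact bound follows. The protocol's list of statistics is open-ended, and the SAP adds SD and quartiles, which that list does not name. It also keeps vital-sign shift tables and the classification of ECGs as normal or abnormal. The early stop and its reason are disclosed, and the SAP's judgement of adequacy has the same basis as the protocol's judgement about 20 patients. Exact intervals on every organ-class and preferred-term row would add many very wide intervals that no document called for.

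Much of this stands. The omission concerns presentation, and intervals on every row are not needed. An open-ended list allows additions, however; it does not remove an item that is named. Nor does it make the declaration in SAP 7.19 correct.

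A reader might go further and infer that dropping the protocol's intervals is what leaves zero or few events open to being taken as proof of safety. The documents do not support that. The intervals the protocol specified were for means and say nothing about event counts. No interval for adverse-event incidence was ever promised, so none was dropped, and restoring the intervals for means would leave a zero-event table unchanged. Neither document sets a safety acceptance rule or treats zero events as proof, and SAP 7.7 excludes formal testing of safety.

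**Conclusion.** Two separate points hold.

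1. The SAP omits intervals that the protocol specified for mean vital signs, their changes from baseline, and mean ECG results. SAP 7.19 is therefore wrong as written. This rests on the texts alone and needs no assumption.
2. The adequacy statement in SAP 4.2 has no precision figure behind it, and neither document gives an interval for adverse-event proportions. If 16 patients were analysed, zero events would be compatible with a true rate of up to about one in five (20.6% two-sided). Within a disease group of 8 it would be compatible with more than one in three (36.9% two-sided).

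The figures in the second point are conditional. Sixteen is the floor for evaluable patients, and a larger Safety Set would tighten the limits. Eight per group assumes that the 1:1 ratio survived early stopping. One-sided limits should be compared only with one-sided limits, and two-sided with two-sided. The early stop is not the main source of the imprecision, most of which was already present at 20. The point merits correction because the remedy is specific and cheap; it does not invalidate the safety analysis.

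**What to change.** - **SAP 7.10, 7.11 and Tables 14.3.8.1 and 14.3.9.2:** restore the 95% confidence intervals for the means that the protocol specifies, including change from baseline. Otherwise, correct SAP 7.19 to declare and justify their omission.
- **SAP 4.2:** replace the adequacy statement with the final Safety Set number, overall and by disease group, and the event rate that zero events at that number would exclude. Say whether the limit is one- or two-sided.
- **Table 14.3.1.1:** add exact (Clopper-Pearson) 95% intervals to the subject percentages. Table 14.3.1.2 can stay as it is.

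The cost is revised SAP wording and a few table columns, with no new data. The statement on sample size becomes less favourable.

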4.3 Enrolment

For the purpose of this study, an “enrolled patient” is a patient who has signed the informed consent and meets all inclusion and exclusion criteria to participate in the study.

Patients with RA will be diagnosed based on ACR/EULAR10 (Classification Criteria for Rheumatoid Arthritis) and will thereafter be evaluated with DAS 28 (Disease Activity Score Calculator for Rheumatoid Arthritis). Patients with AS will be diagnosed based on the ASAS (Classification Criteria for Axial and Peripheral Spondyloarthritis). Each patient will be anonymized and identified with a patient ID number. A unique subject identification number (Patient ID) will be assigned at the start of the Screening Period to each subject who signs the informed consent form until the study termination of the patient. This number will identify the subject throughout the study. Patient IDs will include the 2-digit country code number (SW) and a 3-digit subject number (ex: SW001 for first subject in). In both groups of patients – i.e. RA and AS patients – the introduction of a Bi-DMARD (biological disease-modifying antirheumatic drug) treatment should be indicated at the moment of inclusion in the study. The Bi-DMARD therapy should start on Day 2 of the study. RA patients must have been treated at

least with one DMARD (methotrexate, leflunomide and sulfasalazine) or a combination of them in the last 3 months – before inclusion – and this/these DMARD(s) will be continued in this study. Otherwise, RA patients must have been previously treated with Bi-DMARD before administration of the new Bi-DMARD treatment. The non-response of the previous Bi-DMARD treatment must be documented. AS patients must at least have been treated with NSAID in the last 3 months before inclusion and they should be under the same NSAID treatment during the last 4 weeks before inclusion. For RA patients, anti-tumour necrosis factor (TNF) antibodies, anti-interleukine 6 (IL-6) antibodies and abatacept therapies are to be considered and are authorized in Switzerland as first line Bi-DMARD agents in RA. On the contrary, anti-CD 20 positive lymphocytes antibodies can only be used, if one anti-TNF therapy failed. In the AS patients group, only anti-TNF antibodies can be considered, if NSAID are not sufficient. Ten patients enrolled in the study will be asked to participate in a dosimetry and PK sub-study, irrespective of the group they are part of (RA or AS).

The patient is free to withdraw from the study for any reason and at any time without giving reason for doing so and without penalty or prejudice. It is also possible that the Sponsor or Swissmedic request termination of the study if there are concerns about conduct or safety.

A patient may be withdrawn from the study if:

- A serious adverse event (SAE) occurs.
- The patient fails to comply with the evaluations or other requirements of the study.
- The patient starts treatment with one of the medications disallowed. The final decision to withdraw a patient who starts treatment with disallowed medication will be made by the Sponsor following consulting of the Investigator.

A patient must be withdrawn from the study if:

- The Investigator considers it, for safety reasons, to be in the best interest of the patient.
- The patient withdraws his/her consent.
- The patient is pregnant.

If withdrawal occurs for any reason, the Investigator must determine the primary reason for a patient's withdrawal from the study. The date and reason for discontinuation must be documented in the CRF. For patients who are lost to follow-up (i.e., those patients whose status is unclear because they fail to appear for study visits without stating an intention to withdraw), the Investigator should show 'due diligence' by documenting in the source documents steps taken to contact the patient, e.g., dates of telephone calls, registered letters, etc.

4.4 Treatment

The single dose vial (rhAnnexin V-128: 0.40 mg) will be reconstituted with 740 MBq (20 mCi) of ^{99m}Tc . The labelling reaction requires 90 minutes and the reconstituted radiolabelled product is stable for 6 h. For the purpose of this study, it is recommended to administer the reconstituted solution within 4 hours after completion of the labelling reaction. The drug is administered at a dose of 250 MBq as a single intravenous bolus over 10-20 seconds at Day 1 and at 6 weeks (42 days) +/- 2 weeks after the first administration.

4.5 Inclusion/Exclusion Criteria

4.5.1 Inclusion Criteria

1. Patients diagnosed with RA based on ACR/EULAR 2010 criteria (score ≥ 6), OR Patients diagnosed with AS based on the ASAS criteria. Patients with RA must have serology assessment performed and documented at the time of enrolment.
2. Patient with RA active disease (DAS $> 2,6$) and the introduction of a Bi-DMARD treatment should be indicated. RA patients must at least have been treated with DMARD (methotrexate, leflunomide and sulfasalazine) or combination of these treatments for at least 3 months. Treatment will be pursued while on study. OR RA patients must have been previously treated with Bi-DMARD before initiation of the new Bi-DMARD treatment. The non-response of the previous Bi-DMARD treatment must be documented. OR Patients with ankylosing spondylitis with insufficiently controlled disease while under NSAID and indication for Bi-DMARD. These patients must be under NSAID for at least 3 months and 99mTc-rhAnnexin V-128 in patients with rheumatoid arthritis or ankylosing spondylitis Protocol Amendment n°4, 16 December 2014 Page 26 of 67 under the same NSAID for at least 1 month prior to enrolment.
3. ≥ 18 years old
4. Karnofsky performance status $\geq 80\%$
5. Negative Pregnancy test for women with childbearing potential
6. For women with childbearing potential, use of two reliable means of contraception (e.g., hormonal contraceptive, patch, vaginal ring, intrauterine device, associated with other barrier method of contraception such as the use of condoms), throughout their participation in the study
7. Absence of ECG anomaly
8. Written ICF signed

